### 6. Describe all the procedures chronologically, from screening/enrollment through study closeout, which will be completed in the research project.

Patients who are interested and eligible to participate in the study will be enrolled and will read and sign the study informed consent prior to surgery.

Participants will have an in depth discussion with our refractive surgery coordinator regarding refractive surgery. Patients will choose LASIK/PRK surgery based on our standard pre-operative discussion that is provided to all patients. As is standard for laser refractive

candidates, the advantages and disadvantages of LASIK/PRK compared to the other refractive surgical options will be discussed.

Following patient selection of their preferred type of refractive procedure they will be randomized as discussed below, and only patients who elect for LASIK/PRK will be included in our study.

Prior to surgery, one eye from each patient will be randomly assigned to receive either Wavefront optimized or Topography Guided treatment. Each patient in the study will have a fellow eye enrolled in the other treatment group. Patients will either receive LASIK treatment or PRK treatment in both eyes but the eyes will be randomized to topography guided or wavefront optimized forms of treatment.

All surgical procedures will be performed according to the standard of care and the surgeons' standard practices. The study outcome measures are standard of care for pre-operative and post-operative evaluation of refractive surgery patients.

The primary outcome measures will be visual acuity at the pre-operative and post-operative and post-operative time points.

Study outcome measures will be evaluated for each treated eye of each subject at each study time point. Additional examinations between study time points may be performed as necessary according to the surgeon's usual care, but will not be considered part of the study data. Patients have a right to withdraw at any time and future medical care will not be influenced by their lack of participation.

If enhancement surgery is deemed necessary and performed during the one-year post-operative period, study data collection will end for that eye at the time of the enhancement. All prior collected data will be included in the statistical analysis.

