**Eyes will be evaluated with the following standard of care procedures:**

- pupil size measured in mesopic format: pre-operative only
- corneal pachymetry: pre-operative only
- uncorrected visual acuity: pre-operatively and post-operative Day 1 (+1 day), Week 1 (+/- 3 days), Month 1 (+/- 10 days), Month 3 (+/- 1 month), Month 6 (+/- 1 month) and Month 12 (+/- 1 month).
- best corrected visual acuity and manifest refraction: pre-operatively and post-operative Month 1 (+/- 10 days), Month 3 (+/- 1 month), Month 6 (+/- 1 month) and Month 12 (+/- 1 month)

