**Patients will also be evaluated with the following procedures for research purposes only:**

Contralateral Eye Survey (developed by Moran Eye Center cornea specialists): post-operative Month 3 (+/- 1 month)

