**8. Is there a safety monitoring plan for this study?**

Yes  No

**9. Provide a summary of the statistical methods, data analysis, or data interpretation planned for this study. Factors for determining the proposed sample size (e.g., power) should be stated.**

Standard statistics will be calculated and used to describe the two treatment groups in terms of all study variables. Statistics will be compiled for each variable at the study time points listed in the data collection protocol. Patients withdrawn from the study prior to surgery will not be included in the data analysis and will be replaced in the enrollment group. For eyes that require enhancement surgery, only data collected prior to the enhancement surgery will be included in the statistical analysis.

Power calculations for this study are based on similar prospective, randomized contralateral eye laser refractive studies comparing wavefront optimized and wavefront guided treatments. Previously published contralateral eye studies demonstrated statistically significant results for similar endpoints as our study by including in the range of 70-100 patients for each treatment group. To ensure sufficient patient numbers accounting for 20-30% drop out, including patients that may need enhancement surgery and may not be able to complete the study.

References:

PI: [name]

Submitted: 10/25/2016

**Title:** Outcomes of topography-guided laser-assisted in situ keratomileusis (LASIK) and phororefractive keratectomy (PRK) compared to wavefront optimized LASIK and PRK

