**Please specify:**

There is no formal data and safety monitoring board for this study. All treatments, procedures, and testing being performed in the study are within the standard of care and treatment for LASIK patients. The study does not put study participants at any known increased risk beyond that normally assumed by patients undergoing LASIK or PRK outside the study. The investigators feel that the standard processes for identifying and reporting adverse events (AE) are sufficient to safeguard the well-being of study participants.

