**b. Under what conditions will the study be modified or stopped?**

The study regimen would be modified or stopped if medically appropriate.

**5. How often will the data and events be reviewed by the monitoring entity (e.g., after every 5 submits, monthly, quarterly, twice a year, etc.)?**

Data will be reviewed after the first 5 participants are enrolled and every 6 months following. Adverse events will be reviewed as they occur.

**Title:** Outcomes of topography-guided laser-assisted in situ keratomileusis (LASIK) and phororefractive keratectomy (PRK) compared to wavefront optimized LASIK and PRK

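### Complications that resolve between visits, or do not lower acuity at one, never enter the by-treatment results, so complication rates in topography-guided and wavefront optimized eyes cannot be reliably compared as written

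*Combined protocol and SAP*

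**What the plan says.** Five parts of the combined protocol and SAP bear on this.

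- **Unscheduled examinations (Study Information, item 6, chronological procedures).** Extra examinations outside the visit schedule "may be performed as necessary according to the surgeon's usual care, but will not be considered part of the study data".
- **Scheduled eye evaluations (same item).** The list is mesopic pupil size, pachymetry ("corneal pachymetry: pre-operative only"), uncorrected acuity, best corrected acuity and manifest refraction. Uncorrected acuity is taken pre-operatively, at Day 1 and Week 1, and at Months 1, 3, 6 and 12. Best corrected acuity and refraction are taken pre-operatively and at Months 1, 3, 6 and 12. A contralateral eye survey is added at Month 3; its items are not given.
- **Enhancement (items 6 and 9).** Enhancement within the first year ends data collection for that eye, and only earlier data from that eye are analysed.
- **Analysis (item 9).** "Standard statistics will be calculated and used to describe the two treatment groups in terms of all study variables". The statistics are tied to the time points in the data collection protocol.
- **Safety Monitoring Plan (items 1, 2, 3 and 5).** There is no formal board. The investigators consider that "standard processes for identifying and reporting adverse events (AE) are sufficient to safeguard the well-being of study participants". Actual vision is compared with expected vision, a safety analysis follows if concerns arise, and each such analysis produces a report. Data are reviewed after the first 5 participants and then every 6 months. "Adverse events will be reviewed as they occur".

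**The concern.** A patient with a problem in one eye is likely to come back between scheduled visits. Those are the examinations that item 6 keeps out of the study data, and the scheduled list has no field in which a complication could be entered afterwards. Followed literally, an eye with an event that appeared and cleared between visits is analysed as an uneventful eye with its next scheduled acuity.

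This bears on the trial's own aim. The objective (Study Purposes and Objectives) is to learn whether equivalent visual outcomes are achievable with both treatments, and Risks and Benefits, item 2 speaks more broadly of equivalent patient outcomes. Risks and Benefits, item 1 names different results in the two eyes as the risk of randomization. The Background says wavefront optimized treatment has long been used at the institution, while the tools for topography-guided treatment were acquired recently. A reader of an equivalence conclusion will reasonably ask whether complications differed. Each patient has one eye on each treatment, so the design could answer with a within-patient count, but the plan does not collect what that count needs.

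**Working it through.** The plan states no figure on this point, so there is none to reproduce. The check traces how a complication could reach the by-treatment results and then counts the days outside the visit windows.

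**Routes into the results**

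1. *Found at an unscheduled examination.* Excluded from the study data by item 6.
2. *Found at a scheduled visit.* None of the five listed evaluations is a complication or adverse event item. The finding can appear only through its effect on acuity or refraction.
3. *Through best corrected acuity.* This is measured per eye, but first at Month 1 post-operatively and then at Months 3, 6 and 12. It shows a loss still present at one of those visits. Before Month 1 only uncorrected acuity is taken (Day 1 and Week 1), and a low value there does not identify its cause.
4. *Through enhancement.* Because enhancement ends data collection for the eye concerned, it must be known by eye. Item 9 uses it only to cut off data; no count by treatment is planned.
5. *Through the Month 3 survey.* Its content is not given, so it can be neither relied on nor ruled out.
6. *Through the Safety Monitoring Plan.* Events are identified, reported and reviewed, but no recording by eye or by assigned treatment is stated, and item 9 does not bring adverse events into the statistics.

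Routes 3 and 4 are the only ones that clearly give eye-level information. Neither captures a transient event, or one that does not lower acuity at a visit.

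**Days outside the visit windows**

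Inputs: the windows in item 6, and a month taken as 30.4 days (assumption). Window limits are rounded to whole days, and the count stops at Day 365.

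| Visit | Window (days) | Days covered |
|---|---|---|
| Day 1 (+1) | 1 to 2 | 2 |
| Week 1 (±3 days) | 4 to 10 | 7 |
| Month 1 (±10 days) | 20 to 40 | 21 |
| Month 3 (±1 month) | 61 to 122 | 62 |
| Month 6 (±1 month) | 152 to 213 | 62 |
| Month 12 (±1 month) | 334 to 365 | 32 |

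Covered: 2 + 7 + 21 + 62 + 62 + 32 = 186 days. Uncovered: 365 − 186 = 179 days, and 179 / 365 = 49%.

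The gaps are Day 3 (1 day), Days 11 to 19 (9), Days 41 to 60 (20), Days 123 to 151 (29) and Days 214 to 333 (120), which again total 179. The last gap, between the Month 6 and Month 12 windows, makes up 120 / 179 = 67% of the uncovered time.

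This is a count of calendar days. Turning it into missed events would need the rate and timing of complications, and the documents give neither.

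**The case against.** **The sentence on unscheduled examinations may be meant narrowly.** It follows directly on the statement that outcome measures are evaluated at each study time point, so it may only keep off-schedule measurements out of the outcome dataset. Adverse events have their own section. This is a fair reading, and for acuity the rule is sensible. The gap remains even so: no adverse event is listed as a study variable, and item 9 summarises only study variables at the listed time points.

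**A reader might infer that the two treatments cannot be compared on safety at all.** The documents do not support that. Best corrected acuity is measured per eye at four post-operative visits and enhancement is known per eye, so a limited comparison is possible, and it covers the events that matter most to lasting vision.

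**A reader might also infer that adverse events go unrecorded, or are only ever handled case by case.** The Safety Monitoring Plan provides for identifying, reporting and reviewing them, for periodic data review, and for a safety analysis with a report. What it does not state is recording by eye or a tabulation by treatment.

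**Comparing complications is not a stated aim.** The hypothesis and the only named outcome concern uncorrected acuity, and both treatments are described as FDA approved and within the standard of care. This stands: the acuity comparison does not depend on the point. It limits the weight of the point but does not remove it, given the wider language of equivalent patient outcomes.

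**Conclusion.** The point holds in a limited form. As written, complications that are transient or do not reduce acuity at a scheduled visit stay out of the by-treatment results, and complication rates in the two groups of eyes cannot be reliably compared. Lasting loss of best corrected acuity and enhancement are identifiable by eye; enhancement is not scheduled to be counted by treatment.

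About half of the first 365 days (179, assuming 30.4-day months) lie outside any visit window. It would be tempting to read this as half of all complications being missed, or to say that none would be captured. Neither follows: days are not events, a lasting effect on acuity would still be seen at a later visit, and the documents give no rate or timing from which to estimate the loss.

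The conclusion rests on the scheduled list in item 6 being complete, and on the Month 3 survey not serving as a complication record. The primary acuity comparison is unaffected. This is an inexpensive improvement that should be made, because without it an equivalence conclusion lacks its safety counterpart.

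**What to change.** 1. **Study Information, item 6.** Keep the rule that acuity from unscheduled examinations is not used for the acuity endpoint. Add that eye-specific adverse events and complications found at any examination, scheduled or unscheduled, through Month 12 are study data, recorded by eye with date, type and resolution.
2. **Study Information, item 9.** Add a descriptive table of the number of eyes with each type of event, and with enhancement, by treatment. Beside it, give the number of patients with an event in one eye only, split by the treatment that eye received. That split uses the pairing directly.
3. **Same item.** Say that the table is descriptive and that the trial is not powered for it. The documents give no complication rate from which power could be calculated.

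The cost is some extra abstraction from clinic charts, including notes of unscheduled visits, and one more table. No visit, procedure or change in care is added.

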**Eyes will be evaluated with the following standard of care procedures:**

- pupil size measured in mesopic format: pre-operative only
- corneal pachymetry: pre-operative only
- uncorrected visual acuity: pre-operatively and post-operative Day 1 (+1 day), Week 1 (+/- 3 days), Month 1 (+/- 10 days), Month 3 (+/- 1 month), Month 6 (+/- 1 month) and Month 12 (+/- 1 month).
- best corrected visual acuity and manifest refraction: pre-operatively and post-operative Month 1 (+/- 10 days), Month 3 (+/- 1 month), Month 6 (+/- 1 month) and Month 12 (+/- 1 month)

**Patients will also be evaluated with the following procedures for research purposes only:**

Contralateral Eye Survey (developed by Moran Eye Center cornea specialists): post-operative Month 3 (+/- 1 month)

**7. Are all procedures for research purposes only (non-standard or non-standard of care procedures)?**

Yes  No

**If no, list the procedures that are performed for research purposes only (non-standard or non-standard of care procedures):**

All procedures are considered within the standard of care for laser refractive surgery and will be billed to patients in the usual manner; however, participants will be eligible for a reduced study fee for their surgery and post-operative care. Laser refractive surgery is considered cosmetic surgery and is never billed to insurance. The refractive surgery charge includes standard post-operative examinations up to one year.

If enhancement surgery is deemed necessary during the one-year post-operative period, this will be included based on the patient's initial fee, as is standard of care. Any other costs related to the management of adverse events, or if additional refraction correction is necessary at some time after the one-year postoperative period, will remain the patient's responsibility and are not included in the study surgery fee.

Randomization, data collection and analysis are being done for research purposes only.

**8. Is there a safety monitoring plan for this study?**

Yes  No

**9. Provide a summary of the statistical methods, data analysis, or data interpretation planned for this study. Factors for determining the proposed sample size (e.g., power) should be stated.**

Standard statistics will be calculated and used to describe the two treatment groups in terms of all study variables. Statistics will be compiled for each variable at the study time points listed in the data collection protocol. Patients withdrawn from the study prior to surgery will not be included in the data analysis and will be replaced in the enrollment group. For eyes that require enhancement surgery, only data collected prior to the enhancement surgery will be included in the statistical analysis.

Power calculations for this study are based on similar prospective, randomized contralateral eye laser refractive studies comparing wavefront optimized and wavefront guided treatments. Previously published contralateral eye studies demonstrated statistically significant results for similar endpoints as our study by including in the range of 70-100 patients for each treatment group. To ensure sufficient patient numbers accounting for 20-30% drop out, including patients that may need enhancement surgery and may not be able to complete the study.

References:

PI: [name]

Submitted: 10/25/2016

**Title:** Outcomes of topography-guided laser-assisted in situ keratomileusis (LASIK) and phororefractive keratectomy (PRK) compared to wavefront optimized LASIK and PRK

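### Eyes are randomised within patient, but the analysis text only describes each treatment group and gives no interval for the within-patient difference

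*Combined protocol and SAP*

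**What the plan says.** The design is paired. Section 4, item 6 (procedures) randomises one eye of each patient and adds: "Each patient in the study will have a fellow eye enrolled in the other treatment group". Study Purposes and Objectives and Background and Introduction both describe a comparison between fellow eyes. The stated hypothesis is that uncorrected acuity will be the same under the two treatments.

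The analysis text is section 4, item 9: "Standard statistics will be calculated and used to describe the two treatment groups in terms of all study variables". It adds that statistics will be compiled for each variable at each study time point. It names no within-patient difference, confidence interval, paired test or model that links the two eyes, and no other section supplies one.

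On enhancement surgery, item 6 says "study data collection will end for that eye at the time of the enhancement" and then "All prior collected data will be included in the statistical analysis". Item 9 agrees: "only data collected prior to the enhancement surgery will be included in the statistical analysis". Item 9 also allows for losses, "accounting for 20-30% drop out, including patients that may need enhancement surgery". Neither item says how a pair is analysed once one eye has stopped contributing data.

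**The concern.** The question is whether fellow eyes come out the same. Answering it takes an estimate of the difference between a patient's two eyes and an interval of the right width. That width depends on the correlation between fellow eyes, which separate group means and SDs do not contain. An analyst who worked only from item 9 could therefore treat the arms as two independent groups and lose the precision that the design was chosen to give.

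A second issue is separate and conditional. Data stop for the enhanced eye only. If eyes with poor acuity are the ones enhanced, the by-visit group means at later visits leave out the poorest eyes, and more of them from the worse arm. A true difference then looks smaller than it is. In a trial whose hypothesis is sameness, that shrinkage leans toward the hypothesis.

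**Working it through.** **Inputs from the documents.** About 400 participants (section 3, item 4) and 20-30% drop-out (section 4, item 9). These give 400 × 0.70 = 280 or 400 × 0.80 = 320 complete pairs. The documents state no alpha, SD, fellow-eye correlation, true difference or margin, so there is no stated precision figure to reproduce.

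**Assumptions, for illustration.** Two-sided alpha 0.05; SD 0.15 logMAR in each arm (0.20 as a variant); fellow-eye correlation ρ = 0.3, 0.5, 0.7.

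**Step 1: standard errors.** Paired: SD × √(2(1−ρ)/n). Arms treated as independent: SD × √(2/n). The ratio is 1/√(1−ρ), and the true size of a nominal 5% unpaired test is 2(1−Φ(1.96/√(1−ρ))).

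| | ρ = 0.3 | ρ = 0.5 | ρ = 0.7 |
|---|---|---|---|
| SE too large by a factor of | 1.20 | 1.41 | 1.83 |
| True size of the unpaired test | 1.9% | 0.56% | 0.03% |
| 95% half-width, 280 pairs: unpaired 0.025, paired | 0.021 | 0.018 | 0.014 |
| 95% half-width, 320 pairs: unpaired 0.023, paired | 0.019 | 0.016 | 0.013 |

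**Step 2: power to detect a difference d** (280 pairs, SD 0.15). Power ≈ Φ((d − 1.96 × SE used)/paired SE), because the estimate varies with the paired SE whichever SE the analyst uses. Example at ρ = 0.5 and d = 0.02: the unpaired SE is 0.0127 and the paired SE 0.0090. Unpaired: Φ((0.02 − 0.0248)/0.0090) = 29%. Paired: Φ(0.02/0.0090 − 1.96) = 61%.

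| True difference | Unpaired, ρ = 0.3/0.5/0.7 | Paired |
|---|---|---|
| 0.02 | 32/29/24% | 47/61/82% |
| 0.03 | 69/72/77% | 81/92/99% |
| 0.05 | at least 99% | at least 99% |

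**Step 3: power to show equivalence when the true difference is 0** (90% interval inside ± margin M, 280 pairs). Power = 2Φ((M − 1.645 × SE used)/paired SE) − 1.

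| Margin, SD | Unpaired, ρ = 0.3/0.5/0.7 | Paired |
|---|---|---|
| 0.03, 0.15 | 61/69/81% | 76/91/99% |
| 0.04, 0.15 | 93/97/99% | 97/99.5/100% |
| 0.05, 0.15 | at least 99% | at least 99% |
| 0.05, 0.20 | 88/94/98% | 94/99/100% |

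**Step 4: enhancement losses, by simulation (illustrative only).** Set-up: 400 patients; mean acuity 0 logMAR; SD 0.15; visits at Months 1, 3, 6 and 12; the three ρ values with within-eye correlations 0.6, 0.7 and 0.85; 10% of patients lost at random after Month 3. An eye's later visits are removed once its Month 3 or Month 6 value exceeds 0.20 or 0.30 logMAR. These cut-offs are a simulation device, not a clinical rule. There are six cells for each true difference, with 61-85% complete pairs at Month 12.

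| Month 12 estimate | True 0.030 | True 0.050 |
|---|---|---|
| Separate group means | 0.020-0.026 | 0.033-0.043 |
| Complete pairs only | 0.026-0.029 | 0.043-0.048 |
| Repeated-measures model, all visits | 0.030 | 0.050 |

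With no true difference, all three are near zero. The repeated-measures runs used known variances and no covariates. A smaller check with estimated variances (80 runs, ρ = 0.5) gave 0.0305 and 0.0499. If the decision to enhance rests on an examination outside the study data, the repeated-measures model gives 0.028-0.030 for a true 0.030, so most of the bias goes but not all.

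**The case against.** The strongest reply is that the harm depends on an analysis nobody has proposed. Every description of the design is a fellow-eye comparison, a Contralateral Eye Survey is planned, and the sample-size text rests on "similar prospective, randomized contralateral eye laser refractive studies". A reader might infer from item 9 that the plan chooses an unpaired test. It does not: it is silent on method, in a form field that asks only for a summary. That stands. Citing contralateral-eye studies for the sample size is still not an analysis rule.

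A reader might also infer that the plan gives no estimate of the treatment effect at all. That goes too far. The difference of the two group means is a point estimate, and with complete pairs it equals the mean paired difference exactly. What is missing is its interval.

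Nor does ignoring the pairing inflate type I error. With positive correlation the test is conservative, and at a difference or margin of 0.05 with SD 0.15 nothing material is lost.

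The enhancement issue is informative missingness rather than pairing, since a complete-pair analysis is shrunk too. The eye-level stopping rule already implies that the fellow eye is kept. The simulated sizes depend on an assumed mean acuity and on cut-offs that the documents do not give. At a true 0.030, the 0.30 cut-off loses about 16-18% of pairs and the 0.20 cut-off about 30-36%, against the planned 20-30%. The largest shrinkage comes only from the heavier losses. These objections limit the size of the point but do not remove it.

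**Conclusion.** The point holds as a gap that should be closed before analysis. Item 9 does not state the contrast that the design and objective call for, and gives no valid interval for it. Comparing the arms as separate groups would widen the standard error by 1/√(1−ρ), or 1.20 to 1.83 times over ρ 0.3 to 0.7. The loss is material for differences of about 0.02-0.03 logMAR or a margin of 0.03 at SD 0.15 and 280 pairs. It is negligible at 0.05 with that SD and modest at 0.05 with SD 0.20. SD, ρ, differences and margins are all assumptions.

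The shrinkage from enhancement is a second, conditional point. Its direction follows if enhancement tends to follow poor acuity, for which the documents give no criterion. Its size is illustrative only. A reader might infer that the trial's estimate will be biased; the documents do not support that, and with no true difference no bias arises. The omission is certain from the text, and the bias figures are not.

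**What to change.** In section 4, item 9, state:

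> The treatment comparison is the within-patient difference (topography-guided eye minus wavefront-optimized eye) in uncorrected acuity, converted from Snellen to logMAR, at [one named post-operative visit], with its confidence interval. The analysis accounts for the pairing of eyes and adjusts for pre-operative eye-level acuity and refraction. Visits before an enhancement are included, later visits of that eye are treated as missing, and the fellow eye is kept. The mean difference on complete pairs at the named visit is reported as a check.

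A suitable choice is a repeated-measures mixed model over the post-operative visits, with treatment, visit and their interaction as fixed effects and patient and eye-within-patient as random effects. Other paired methods would close the main gap. This one also uses an enhanced eye's earlier visits, as items 6 and 9 intend. The covariates gain precision from data already collected and do not correct an error. The group descriptive tables can stay.

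The cost is wording and a little more analysis work, with no new patients, visits or data. The downside is reliance on a missing-at-random assumption. Item 6 allows that "Additional examinations between study time points may be performed as necessary" and keeps them out of the study data, so an enhancement decided on such an examination would strain that assumption. The complete-pair result should therefore be shown beside the model.

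### Visit-by-visit statistics leave the earlier fellow-eye differences of patients lost after surgery out of the Month 6 and 12 summaries: some precision is lost, and bias arises only under certain reasons for leaving

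*Combined protocol and SAP*

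**What the plan says.** All of the analysis rules are in section 4 (Study Information), items 6 and 9.

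- **Type of analysis.** Item 9: "Standard statistics will be calculated and used to describe the two treatment groups in terms of all study variables". It continues: "Statistics will be compiled for each variable at the study time points listed in the data collection protocol". No paired or longitudinal model, imputation or sensitivity analysis is named.
- **Expected loss.** Item 9 plans the numbers with "accounting for 20-30% drop out, including patients that may need enhancement surgery and may not be able to complete the study".
- **Missing data that are covered.** For withdrawal before surgery: "Patients withdrawn from the study prior to surgery will not be included in the data analysis and will be replaced in the enrollment group". For enhancement, item 6 says that "study data collection will end for that eye at the time of the enhancement" and that "All prior collected data will be included in the statistical analysis".
- **Missing data that are not covered.** Nothing says how a patient lost after surgery is handled.
- **Schedule.** The evaluations listed under item 6 include "uncorrected visual acuity: pre-operatively and post-operative Day 1 (+1 day), Week 1 (+/- 3 days", and then Months 1, 3, 6 and 12. That makes six post-operative acuity visits.
- **Size and hypothesis.** Section 3, item 4 gives about 400 participants. Section 1, item 6 hypothesises that acuity is the same with both treatments and states no margin. No primary visit is named.

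**The concern.** The plan's answer to loss is to enrol enough patients. That protects the number of pairs but does nothing for the estimate. A patient who misses Month 12 will usually have several earlier fellow-eye differences on file, and these help to predict the missing one. A Month 12 statistic compiled on its own cannot use them.

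Two things could be at stake. The first is precision, which is given up although the data have been collected. The second is bias, if the pairs still present at Month 12 differ systematically from those that left. Because the hypothesis is one of sameness, a shift toward zero would favour it.

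**Working it through.** **Inputs from the documents.** N = 400; loss m = 0.20 to 0.30; six post-operative visits; one eye per treatment in every patient.

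**Inputs assumed.** The documents give no standard deviation or correlation. Assumed: SD of the fellow-eye difference (s) 0.10-0.15 logMAR, and correlation r between a patient's earlier and Month 12 differences of 0.5-0.8 for precision and 0.5-0.7 for bias.

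**Count.** 0.20 × 400 = 80 and 0.30 × 400 = 120 patients, leaving 320 and 280 pairs. Enhancement cases sit inside the 20-30%, so these are upper bounds on patients lost to follow-up.

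**Precision** (loss unrelated to outcome, large-sample formulas).

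- Pairs present at Month 12 only: variance = s²/[n(1 − m)].
- One earlier visit also used: variance = (s²/n)[1 + (m/(1 − m))(1 − r²)].
- The ratio of the two is 1 − m·r², so the saving is m·r².

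| m | r | Present only (× s²/n) | With earlier visit (× s²/n) | Saving |
|---|---|---|---|---|
| 0.20 | 0.5 | 1.250 | 1.188 | 5% |
| 0.30 | 0.8 | 1.429 | 1.154 | 19% |

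The saving is proportional to m, so if only half of the assumed loss occurs, the saving halves.

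**Bias.** Simulations of 2,000,000 pairs compared the mean Month 12 difference among pairs still present with the truth. In the first two tables' worth of cases below that use an odds ratio, loss averages 25% (300 pairs) and the odds of leaving rise 1.5-2.0 fold per SD of the Month 3 difference.

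| Why patients leave | True difference | Bias (logMAR) |
|---|---|---|
| Unrelated to outcome, or the average of both eyes | 0 or 0.05 | nil |
| Size of the between-eye difference, whichever eye is worse | 0 | nil (0.0002 or less) |
| Same | 0.02 | 0.0007-0.0020 toward zero |
| Same | 0.05 | 0.0019-0.0050 toward zero |
| Signed difference, so one treatment's eye | any | 0.0048-0.0166, either direction |

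The first row comes from a second simulation with other assumptions: SD 0.10 per eye, equal in both treatments; between-eye and early-late correlations both 0.6; 20% or 30% loss. For loss driven by the worse eye with a true difference of 0.05, that simulation gave 0.003-0.004 toward zero. For loss driven by one treatment's eye it gave 0.006 (20% loss) to 0.008 (30% loss).

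In standard errors at 300 pairs, the last row spans 0.0048/(0.10/√300) = 0.0048/0.0058 = 0.8 to 0.0166/(0.15/√300) = 0.0166/0.0087 = 1.9.

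An estimate that also used the earlier fellow-eye data was within 0.0003 of the truth in every case. In these simulations leaving depended only on observed early values, which is the condition under which such a model works.

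**The case against.** **The largest bias needs an unusual mechanism.** Patients would have to leave when the eye of one particular treatment is worse and stay when the other eye is equally worse. Nothing in the documents suggests this. A more natural account is dissatisfaction with whichever eye is worse, which gives no bias when there is no true difference. This stands, and the 0.005-0.017 range is the adverse case. Its direction is also unknown: with no true difference it would create a spurious one, which works against the hypothesis.

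**The loss is overstated if 20-30% is read as loss to follow-up.** This stands, as the figure includes enhancement cases and an enhancement ends data for one eye only. The number truly lost is not given.

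**The plan does not say that only attenders are summarised, and earlier data are not thrown away.** This stands as a matter of wording. The attenders-only reading is inferred from separate statistics at each visit with no other rule. Earlier pairs still count at their own visits; they simply do not inform the later ones.

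**The precision gain is not needed.** The 280-320 remaining pairs exceed the 70-100 patients per group that item 9 cites from earlier studies. That limits the importance of the point but is no reason to leave collected data unused.

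**The missing primary visit, margin and paired analysis are more basic gaps.** True. However, a model that reports every visit does not depend on which visit is later called primary.

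**Conclusion.** The point holds as an inexpensive improvement. The plan expects appreciable loss, schedules six post-operative measurements, and states no way to use the early ones when the late ones are missing.

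The firmer cost is precision: a variance 5-19% higher than it need be at Month 12, relative to the plan's present-only variance, given 20-30% loss and correlations of 0.5-0.8. The saving is smaller if part of that loss is enhancement. Bias is conditional: nil under several plausible reasons for leaving, about 0.001-0.005 logMAR toward zero if the worse eye drives leaving and the true difference is 0.02-0.05, and 0.005-0.017 only if leaving follows one treatment's eye. All sizes rest on assumed standard deviations, correlations and odds ratios.

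A reader might infer that drop out unbalances the treatment groups, or that the late results will be biased toward sameness. The documents support neither. A departing patient removes one eye from each group, and nothing in the plan shows why patients would leave.

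**What to change.** In section 4, item 9, replace the visit-by-visit rule for uncorrected acuity with the following.

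1. Convert acuity to logMAR and fit one mixed model for repeated measures to the fellow-eye difference at all post-operative visits, with visit as a factor and unstructured covariance within patient.
2. Report the treatment difference with its 95% CI at each visit from that model.
3. Tabulate complete pairs at each visit, with losses to follow-up shown separately from enhancements.
4. Add a sensitivity analysis that shifts the unobserved differences by a stated range of deltas and shows the late-visit difference and CI at each. A tipping point can be reported only if an equivalence margin is set, because the plan now gives neither a margin nor a decision rule.

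The cost is plan wording, one standard model and the sensitivity runs. No visit, measurement or patient is added.

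There are two downsides. The model assumes that loss is explained by the visits observed; the delta analysis shows how far the result depends on that. And once one eye is enhanced there is no fellow-eye difference, so the model would treat later values as ordinary missing data. Those cases must be reported separately, and the plan should say openly how they are to be interpreted.
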